#### **4.4 Screening Eligibility**

*Note: Title previously read "Screening and Randomization Eligibility". The reference of randomization has been removed due to discontinuation of the placebo treatment in the Double-Blind Treatment Period.*

Subjects will be considered eligible for Part 1 screening if they meet the Part 1 inclusion criteria and do not meet any Part 1 exclusion criteria. Subjects who do not meet eligibility criteria at Part 1 Screening will be considered screen failures; however, subjects may be rescreened for Part 1 if they

- 1) Failed to meet eligibility because of a T-score above 65 on the MASC-10 under Protocol Amendment 1
- 2) Failed to meet eligibility because of being negative on HLA DQB1:0602 under Protocol Amendment 1 or 2
- 3) Failed to meet eligibility because of a T-score at or above 65 on CDI 2:SR[S] under Protocol Amendment 1 or 2 (In this case, permission of the Medical Monitor is required before the subject is rescreened.)

Xyrem® (sodium oxybate) oral solution  
Clinical Study Protocol: 13-005 Amendment 5

Jazz Pharmaceuticals

In addition, rescreening following resolution of transient exclusionary conditions or stabilization of conditions that were exclusionary in the unstable state (e.g., unstable hypothyroidism) is permitted only with the permission of the Medical Monitor.

Under Amendment 5, subjects who re-enroll in the study must complete the Part 2 Screening. Subjects who re-enroll within 2 weeks after completing Visit 15 in Part 1 of the study do not require clinical laboratory tests, a urine drug screen, an alcohol test, or a serum pregnancy test at the Part 2 Screening visit. For these subjects, the screening visit (Visit 17) and the first drug-dispensing visit (Visit 18) may occur on the same day.

## 5 STUDY TREATMENT(S)

### 5.1 Description of Treatment

Xyrem® (sodium oxybate) oral solution, 500 mg/mL

Xyrem Placebo: a sodium citrate solution prepared in equimolar concentration to sodium in the 500 mg/mL Xyrem (sodium oxybate) oral solution and pH adjusted with malic acid (Placebo treatment only applicable to subjects who had already entered the Double-Blind Treatment prior to Amendment 4 becoming effective).

The bioequivalence of the study drug prepared in a flavored diluent versus prepared in water has been evaluated, and bioequivalence has been established. If available, a flavorant that can be added to the water that is used as diluent will be provided for study drug preparation if flavored diluent is requested by the subject/parent/guardian for palatability. Sucralose in the flavorant is equivalent to 28 mg sucralose in 60 mL, or 56 mg per daily intake of Xyrem prepared with flavored diluent. The FDA acceptable daily intake (ADI) for sucralose is 5 mg/kg body weight/day ([Federal Register, Vol. 63, No. 64, 1998](#)) and the European Union ADI is 0 – 15 mg/kg body weight ([SCF/CS/ADDS/EDUL/190 Final 12/9/2000](#)).

### 5.2 Treatment Administered

Subjects who have been titrated to a stable dose of Xyrem prior to study entry will remain on their stable dose and regimen of Xyrem for 3 weeks during the Stable-Dose Period.

Xyrem-naïve subjects entering Part 1 and subjects re-enrolling in Part 2 who have been off Xyrem for  $\geq 1$  month will be titrated on Xyrem over a period of up to 10 weeks. Xyrem doses are administered in two equally divided doses 2.5 to 4 hours apart. Dose initiation and titration will be based on the subject's weight as described in [Table 1](#). Dose adjustment during the Part 1 and Part 2 titration periods will proceed at a rate of  $\leq 1$  g/night/week for subjects  $< 45$  kg, and  $\leq 1.5$  g/night/week for subjects  $\geq 45$  kg, to a dose level no higher than the maximum dose described in [Table 1](#). Once the Investigator is satisfied that the Xyrem dose has been optimized, the subject may enter the 2-week Stable-Dose Period if in Part 1 of the study or continue the Open-Label Continuation Period if in Part 2.

At the end of the Stable-Dose Period, subjects who had entered the Double-Blind Period prior to Amendment 4 becoming effective were randomized 1:1 to receive either Xyrem or Xyrem placebo during the Double-Blind Treatment Period as follows:

Xyrem® (sodium oxybate) oral solution  
Clinical Study Protocol: 13-005 Amendment 5

Jazz Pharmaceuticals

- Xyrem: Active Xyrem will be continued as a double-blind treatment at the stable dose taken and regimen used in the previous 2 weeks
- Placebo: Xyrem placebo will be initiated as a double-blind treatment at a volume and regimen equivalent to that of the stable dose of Xyrem taken in the previous 2 weeks.

During the Double-Blind Period, subjects will remain on the same dosing regimen they used during the Stable-Dose Period, with the exception of PK nights (if applicable) when all subjects have to take two equally divided doses 4 hours apart.

Subjects entering the Double-Blind Treatment Period after Amendment 4 becoming effective will receive open-label Xyrem treatment during this period.

During the Part 1 Open-Label Safety Period and following titration in the Part 2 Open-Label Continuation Period subjects may take two equally divided doses or two unequally divided doses with the exception of PK nights, if applicable. Xyrem dose adjustment due to tolerability and efficacy is permitted. Xyrem dose uptitration is allowed at no more than 1.5 g/night. Only doses that match the printed gradations (lines) on the dosing syringe are permitted.

Study Drug will be dispensed at clinic visits and, if applicable, at intervals specified by State or local regulations. Xyrem doses on PSG and PK nights will be administered by or under the supervision of qualified study site personnel. Each Xyrem dose will be diluted with 60 mL of water. On PK nights, Xyrem doses will be followed by 180 mL of water. Subjects will continue to take their usual nightly dose of Xyrem on non-PSG and non-PK nights.

The actual time of dosing for each dose administered on PSG and PK nights will be recorded.

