**Table 1 Xyrem Dose Initiation and Titration for Xyrem-naïve Subjects**

Subject weight	Initiation dose (taken in two equally divided doses)*	Titration regimen	Maximum total nightly dose
<30 kg	≤2 g/night	≤1 g/night/week	6 g/night
≥30 kg – <45 kg	≤3 g/night	≤1 g/night/week	7.5 g/night
≥45 kg	≤4.5 g/night	≤1.5 g/night/week	9 g/night

\*At bedtime and 2.5 to 4 hours later. For children who sleep more than 8 hours per night, Xyrem may be given after bedtime, while the child is in bed, in two equally divided doses 2.5 to 4 hours apart.

Xyrem dose reduction is allowed for tolerability reasons at any time, at the Investigator's discretion, in any decrement that is a multiple of 0.5 g/night. Stimulant taper and withdrawal may be attempted at the Investigator's discretion during the Open-Label Titration Period.

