3.1.5 Open-Label Safety Period (to allow up to 1 year Xyrem exposure)

Subjects who are eligible to participate in the Open-Label Safety Period will participate in this period for 47 weeks if they entered the study on a stable dose of Xyrem or for a period of 38-45 weeks if they entered as Xyrem naïve, depending on the duration of the titration period in which they participated (45 weeks assumes that the shortest titration period will be 3 weeks for those subjects who reach an optimal response very quickly during titration).

All study procedures and assessments will be carried out according to the planned schedule (changes in Xyrem dose will generally not affect the schedule).

All subjects will be seen in the clinic 4 weeks after the Open-Label Safety Period begins (Visit 5) and then at Weeks 18, 26, 39, and 52 from study entry (Day 1). However, if in the case of subjects who are Xyrem naïve, Visit 5 is within 2 weeks of the Week 18 visit, the first clinic visit of the Open-Label Safety Period will be the Week 18 visit.

Subjects/parent(s)/guardian(s) will be contacted in the interim by phone at Weeks 16, 22, 30, 34, 43, and 48 from study entry (Day 1). A final PSG will be performed at Week 52 or the Part 1 early termination visit (if the subject who terminates early is willing to participate in another PSG night and if they are willing to take Xyrem the evening of the PSG). The Part 1 early termination PSG does not apply for subjects who discontinue before entering the Open-Label Safety Period. Clinicians may schedule clinic or phone visits between protocol-specified clinic visits to ensure subject safety or to accommodate PK visits (if applicable). Additional drug dispensing visits may be added as required by local law or at the Investigator's discretion based on safe drug storage requirements. Stimulants for EDS may be used as adjunctive therapy throughout the trial, and can be adjusted or discontinued as appropriate.

For subjects who had entered the Double-Blind Treatment Period before Amendment 4 was effective, upon entering the Open-Label Safety Period, these subjects will be started at a dose no higher than half the Xyrem dose they received at the end of the Stable-Dose Period or the

Xyrem® (sodium oxybate) oral solution  
Clinical Study Protocol: 13-005 Amendment 5

Jazz Pharmaceuticals

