### 3.1.8 Open-Label Continuation Period (Part 2)

Upon approval of Amendment 5, subjects who have completed Part 1 in the study may participate in Part 2 of the study. Subjects ongoing in the study when Amendment 5 becomes effective may enter Part 2 after completing the Part 1 Open-Label Safety Period, bypassing the 2-week Safety Follow-up Period. These subjects will begin Part 2 at Visit 15. Subjects who have already completed Part 1 of the study may re-enroll in Part 2. Subjects who re-enroll must complete the Part 2 Screening Visit. Subjects must be on a stable dose of Xyrem, or if they have been off Xyrem for  $\geq 1$  month, must be titrated to an effective and tolerable Xyrem dose. For subjects who have been off Xyrem for less than 1 month, titration may also be required per the Investigator's judgment. Subjects will be titrated to Xyrem as described in [Section 3.1.2](#). In Part 2, subjects will have the opportunity to continue open-label Xyrem treatment until the first occurrence of any of the following:

- Up to an additional 2 years
- Until the subject reaches 18 years of age
- Until up to 3 months after the US FDA decision on the addition of pediatric data to the Xyrem US prescribing information (PI)

Safety will be assessed at scheduled visits throughout Part 2. All subjects will be seen in the clinic at the beginning of Part 2 (Visit 15 for subjects continuing and Visits 17 and 18 for subjects re-enrolling) and every 3 months thereafter. Subjects/parent(s)/guardian(s) will be contacted in the interim months by phone. Clinicians may schedule clinic or phone visits between protocol-specified clinic visits to ensure subject safety. Additional drug dispensing visits may be added as required by local law or at the Investigator's discretion based on safe drug storage requirements. For subjects turning 18 years of age, the Part 2 Study Termination visit must be scheduled prior to the subject's 18th birthday.

Subjects who re-enroll and require titration in Part 2 will be titrated on Xyrem to achieve clinical benefit in cataplexy and EDS while maintaining tolerability based on the Investigator's assessment. Following Visit 18 (begin titration), the subject/parent(s)/guardian(s) will be contacted by phone at titration weeks T2, T3, T4, T7, T8, and T10 to determine if additional titration is necessary or to follow up after the subject has reached a stable dose.

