Upon entering the Open-Label Safety Period, all subjects will be started at a dose no higher than half the Xyrem dose they received at the end of the Stable-Dose Period or the initiation dose defined in [Table 1](#), whichever is higher. Subjects will then be titrated up to their optimal dose as tolerated according to the Investigator's judgment (the maximum dose should not exceed the doses defined in [Table 1](#) or the stable dose prior to study entry, whichever is higher, and should not be greater than 9 g/night). Xyrem dose uptitration is allowed at no more than 1.5 g/night.
  - **For subjects entering the Double-Blind Period after Amendment 4 becoming effective:**  
Subjects will continue on in the Open-Label Safety Period at their appropriate dose.
- Collect study drug dispensed at Visit 3 and assess compliance.
- Schedule next visit.

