  - Upon entering the Open-Label Safety Period, all subjects will be started at a dose no higher than half the Xyrem dose they received at the end of the Stable-Dose Period or the initiation dose defined in [Table 1](#), whichever is higher. Subjects will then be titrated up to their optimal dose as tolerated according to the Investigator's judgment (the maximum dose should not exceed the doses defined in [Table 1](#) or the stable dose prior to study entry, whichever is higher, and should not be greater than 9 g/night). Xyrem dose uptitration is allowed at no more than 1.5 g/night.
  - **For subjects entering the Double-Blind Period after Amendment 4 becoming effective:**  
Subjects will continue on in the Open-Label Safety Period at the same dose that they have been taking.
- Schedule next visit.

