#### 7.6.3.2 Visits 18.1, 18.2, 19, 19.1, 20, 20.1 (Phone Calls) Subjects Re-enrolling Who Require Titration

Study activities for Titration Phone Visits 18.1 (Week T2 +3 days), 18.2 (Week T3 +3 days), 19 (Week T4 +3 days), 19.1 (Week T7 +3 days), 20 (Week T8 +3 days), 20.1 (Week T10 +3 days) are as follows:

- Record all AEs that occur after assent was given and the ICF was signed on the AE CRF.
- Record all concomitant medications that were taken after assent was given and the ICF was signed on the concomitant medications CRF.
- Determine if additional dose titration is necessary.
- Determine when the subject will be 18 years of age. Schedule the Part 2 Study Termination Visit to occur *prior to* the subject's 18th birthday.

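### After titration, Section 5.2 limits the size and pace of dose increases only to 1.5 g/night, with no minimum interval and no smaller maximum step below 45 kg

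*Protocol*

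**What the plan says.** **After titration.** Section 5.2 covers the Part 1 Open-Label Safety Period and Part 2 once titration is over. It states "Xyrem dose adjustment due to tolerability and efficacy is permitted. Xyrem dose uptitration is allowed at no more than 1.5 g/night" and requires each dose to match a line on the syringe. It gives no time unit and no weight band, and it does not separate a return to an earlier dose from a move to a new, higher one.

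**During titration.** Table 1 gives "≤1 g/night/week" for both weight bands below 45 kg and 1.5 g/night per week from 45 kg. Section 3.1.2 repeats these rates. Section 5.2 ties them to titration: "Dose adjustment during the Part 1 and Part 2 titration periods will proceed at a rate of" those values.

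**Subjects who entered the Double-Blind Period before Amendment 4.** Sections 3.1.5, 7.1.5 and 7.2.5 restart them at a reduced dose and allow increases of up to 1.5 g/night. The total is capped at the higher of the Table 1 maximum and the pre-study stable dose, and never above 9 g/night. Section 3.1.5 also obliges the investigator to monitor tolerability during up-titration.

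**Later entrants.** Only the entry dose is given. Section 7.1.5 says "Subjects will continue on in the Open-Label Safety Period at their appropriate dose", and Section 7.2.5 says "Subjects will continue on in the Open-Label Safety Period at the same dose that they have been taking".

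**The concern.** During titration the sponsor limits children below 45 kg to increases of 1 g/night, one week apart. Once titration ends both limits lapse, although increases for efficacy remain allowed and may exceed any dose the child has taken before. The protocol gives no reason for the change.

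The interval between increases is the time in which tolerability at the new dose can be seen. The events Section 3.1.5 tells investigators to watch for include respiratory depression, depressed consciousness, confusion, parasomnias and suicidality. No contact is tied to an increase. In Part 1, "changes in Xyrem dose will generally not affect the schedule". In Part 2, families "will be contacted in the interim months by phone", with a clinic visit every 3 months, and the routine calls in Section 7.5.2 cover adverse events, concomitant medication and the 18th-birthday check. In Part 2, the instruction "Determine if additional dose titration is necessary" belongs to the titration calls (Section 7.6.3.2).

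At stake is a dosing-safety rule for children who may be treated for up to 3 years.

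**Working it through.** The plan gives no figure to reproduce, so the check is a comparison of the rules plus simple arithmetic.

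**1. Is there another post-titration limit on size or pace?**

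| Place | Applies to | Maximum step | Interval | Ceiling on total dose |
|---|---|---|---|---|
| Section 3.1.2, Table 1, Section 5.2 | Titration, Parts 1 and 2 | 1 g/night below 45 kg; 1.5 g/night from 45 kg | One week | 6, 7.5 or 9 g/night by weight |
| Sections 3.1.5, 7.1.5, 7.2.5 | Pre-Amendment 4 subjects after the Double-Blind Period | 1.5 g/night, all weights | None | Table 1 maximum or pre-study stable dose; at most 9 g/night |
| Section 5.2 | Part 1 Open-Label Safety Period; Part 2 after titration | 1.5 g/night, all weights | None | Not restated |

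No section supplies an interval, or a smaller step below 45 kg, after titration.

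**2. Step size below 45 kg.** 1.5 / 1 = 1.5, so the permitted step is 50% larger. From 45 kg the step is unchanged at 1.5 g/night and only the weekly interval is lost.

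**3. Step relative to the current dose, below 45 kg.**

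| Current dose (g/night) | Section 5.2 step | Table 1 step |
|---|---|---|
| 3 | 1.5/3 = 50% | 1/3 = 33% |
| 4.5 | 1.5/4.5 = 33% | 1/4.5 = 22% |
| 6 | 1.5/6 = 25% | 1/6 = 17% |

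For comparison, Table 1 itself allows 2 to 3 g/night below 30 kg: 1/2 = 50%.

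**4. Pace of a 3 g/night rise.**
- 30 to <45 kg, from 4.5 to 7.5 g/night at the Table 1 rate: 5.5, 6.5 and 7.5 g on days 0, 7 and 14. That is three steps and at least 14 days from first to last.
- The same rise under Section 5.2: 3/1.5 = 2 steps (6, then 7.5 g), spacing not set.
- 45 kg or more at the Table 1 rate: two steps of 1.5 g on days 0 and 7, at least 7 days. Under Section 5.2: two steps, spacing not set.

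**5. Exposure (illustration only).** Section 1.1.1.1 reports that adult blood levels rise 3.7-fold when the dose doubles from 4.5 to 9 g. Assume a power law that also holds in children; the exponent is then ln 3.7 / ln 2 = 1.89. A step from 4.5 to 6 g multiplies exposure by (6/4.5)^1.89 = 1.7, and a step from 4.5 to 5.5 g by 1.5. With strict proportionality the factors would be 6/4.5 = 1.33 and 5.5/4.5 = 1.22. The conclusion does not depend on this step.

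**The case against.** The strongest reply is that the rule does not stand alone. Section 3.1.5 requires tolerability monitoring and names the events that matter. Total dose is capped. From Week 16 of Part 1, contacts fall every 2 to 5 weeks (Weeks 16, 18, 22, 26, 30, 34, 39, 43, 48 and 52); adverse events are recorded and the C-SSRS, CDI 2 and MASC-10 are administered. Unscheduled visits may be added for safety, Section 6.14 gives stopping rules, and the DSMB reviews respiratory depression and depressed consciousness. Subjects who reach this stage in Part 1 have already been titrated to benefit with tolerability, or have held a stable dose for at least 2 months before screening. A child settled at 4.5 g who then needs 3 g more in quick succession is possible on paper, but nothing in the protocol suggests that it is expected. The investigator may also go more slowly.

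Much of this stands and limits the weight of the point. It does not supply the missing interval or step. The ceiling and the monitoring duty sit in text about pre-Amendment 4 subjects, for whom a 1.5 g/night step mostly means returning to a recently tolerated dose. Section 5.2 is not limited to that case.

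A reader might infer more than the documents support:
- **A contradiction between the two limits.** There is none; they govern different periods.
- **Accumulation of drug.** Section 5.3 gives a half-life of 0.5 to 1 hour.
- **A relative step without precedent.** Table 1 already allows 50%.
- **Untracked drug use, because the dosing diary runs only in Part 1 and asks only whether doses were taken.** Sections 5.9 and 5.10 also use the prescribed dose and the volume returned, and call for action on significant discrepancies.

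**Conclusion.** The point holds as a gap in a stated safety rule. After titration, the only limit on the size and pace of increases is 1.5 g/night. Below 45 kg that is a step 50% larger than the titration rule allows. At every weight the one-week minimum is gone: for a 3 g/night rise, at least 14 days below 45 kg and at least 7 days from 45 kg become no minimum at all.

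This rests on reading Section 5.2 literally. If the sponsor meant a weekly rate, or meant the Section 3.1.5 ceiling and monitoring duty to cover everyone, the text should say so. It would be wrong to infer that post-titration increases are uncapped or unmonitored throughout the study: both safeguards exist, but their stated scope is narrower than that of Section 5.2. No endpoint, estimate or efficacy conclusion is affected, so this is a cheap improvement and not an error in the trial's inference.

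**What to change.** In Section 5.2, where post-titration increases are allowed, state that:

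1. Any increase above a previously tolerated dose follows the Table 1 rate for the child's weight: at most 1 g/night per week below 45 kg and at most 1.5 g/night per week from 45 kg.
2. Steps of up to 1.5 g/night remain allowed when returning to a previously tolerated dose.
3. The dose ceiling and the tolerability monitoring in Section 3.1.5 apply to all subjects in the Part 1 Open-Label Safety Period and in Part 2.

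Aligning the wording of Sections 3.1.5, 7.1.5 and 7.2.5 is tidy but secondary.

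The change adds no visits and does not touch data already collected. Its cost is slower escalation for some children, for example at least 14 days from first to last increase for a 3 g/night rise below 45 kg.

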initiation dose defined in [Table 1](#), whichever is higher. Subjects will then be titrated up to their optimal dose as tolerated according to the Investigator's judgment (the maximum dose should not exceed the doses defined in [Table 1](#) or the stable dose prior to study entry, whichever is higher, and should not be greater than 9 g/night). Xyrem dose up-titration is allowed at no more than 1.5 g/night, and during dose up titration the Investigator must monitor tolerability, which includes AEs observed at night, such as confusion, respiratory depression, sleepwalking and other parasomnias; residual effect and AEs observed during daytime, such as confusion, somnolence, pronounced levels of depressed consciousness, depressed mood and suicidality, anxiety, abuse or misuse of Xyrem, and weight loss.

Subjects may take two equally divided doses or two unequally divided doses with the exception of PK nights (if applicable) when all subjects have to take two equally divided doses 4 hours apart. Xyrem dose adjustment due to tolerability and efficacy is permitted. Only doses that match the printed gradations (lines) on the dosing syringe are permitted.

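### Section 5.2 lets the open-label dose be raised for efficacy with a step limit but no nightly ceiling; the only open-label ceiling is written for subjects who entered the Double-Blind Period before Amendment 4

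*Protocol*

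**What the plan says.** Section 5.2 gives the dosing rule for the Part 1 Open-Label Safety Period and for Part 2 once titration is over: "Xyrem dose adjustment due to tolerability and efficacy is permitted. Xyrem dose uptitration is allowed at no more than 1.5 g/night". It adds that each dose must fall on a printed syringe line. It gives no maximum nightly dose for these periods.

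A maximum for open-label dosing appears in Section 3.1.5. The paragraph opens with "For subjects who had entered the Double-Blind Treatment Period before Amendment 4 was effective, upon entering the Open-Label Safety Period" and describes a restart at no more than half dose (or at the Table 1 initiation dose, if higher), followed by re-titration. It then caps the dose at the Table 1 value or "the stable dose prior to study entry, whichever is higher, and should not be greater than 9 g/night". Sections 7.1.5 and 7.2.5 repeat this cap under a sub-heading for the same earlier entrants. For later entrants, the sub-heading that follows carries no cap:

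- Section 7.1.5: "Subjects will continue on in the Open-Label Safety Period at their appropriate dose"
- Section 7.2.5: "Subjects will continue on in the Open-Label Safety Period at the same dose that they have been taking"

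Table 1 has a column headed "Maximum total nightly dose": 6 g below 30 kg, 7.5 g from 30 to under 45 kg, and 9 g from 45 kg. Section 5.2 ties that maximum to titration, in the sentence beginning "Dose adjustment during the Part 1 and Part 2 titration periods will proceed at a rate of". Section 3.1.8 brings it into Part 2 only for re-enrollers who need titration: "Subjects will be titrated to Xyrem as described in" Section 3.1.2.

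**The concern.** Two Xyrem-naïve children of the same weight and on the same optimized dose face different rules in the open-label year, depending only on whether they reached Visit 3 before or after Amendment 4 took effect. The protocol gives no reason for the difference. In Part 2 the ceiling is not stated for anyone once titration is over.

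Xyrem is a CNS depressant, and the weight bands in Table 1 are the protocol's only weight-based dose limit for children with no earlier dose to rely on. The explicit instruction to watch for respiratory depression, confusion and suicidality during up-titration sits in the same paragraph of Section 3.1.5 as the cap, so its scope is equally narrow. Scheduled Part 2 follow-up is also lighter than in Part 1: monthly calls and three-monthly clinic visits, with no polysomnography and no suicidality or depression scale scheduled after Visit 15.

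**Working it through.** The protocol has no calculated figure to reproduce here. The check is to list every statement that could act as a ceiling, ask whom it binds and when, and then see what one permitted step allows.

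**Step 1: each possible ceiling and its reach**

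| Place | Limit | Whom and when |
|---|---|---|
| Table 1, Section 3.1.2, titration text of 5.2 | 6 / 7.5 / 9 g by weight | Titration periods in Parts 1 and 2 |
| Section 3.1.5, restart paragraph | Table 1 or pre-study dose, at most 9 g | Open-Label Safety Period, pre-Amendment 4 entrants |
| Section 3.1.5, closing paragraph | Syringe lines only | Open-Label Safety Period, all subjects |
| Sections 7.1.5 and 7.2.5, first sub-heading | Same as the 3.1.5 restart paragraph | Pre-Amendment 4 entrants |
| Sections 7.1.5 and 7.2.5, second sub-heading | None | Post-Amendment 4 entrants |
| Inclusion criterion 8 | 9 g | Subjects on Xyrem, at Part 1 entry |
| Inclusion criterion 20 | 9 g | Re-enrollers on Xyrem, at Visits 17 and 18 |
| Section 5.2, open-label text | 1.5 g step, syringe lines | Open-Label Safety Period; Part 2 after titration |

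Two routes into Part 2 bypass Table 1 altogether. Subjects who continue directly from Part 1 are not titrated again, and under Section 7.6.2 neither are re-enrollers who stayed on a stable dose.

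Section 7.6.3.1 also allows adjustment at the investigator's judgment, but it concerns the Part 2 titration period, where the Table 1 maximum applies. It is not part of the gap. The removal rules in Section 6.14 cover intolerable related adverse events, PSG findings judged a risk and unspecified entry criteria. They are not dose ceilings.

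**Step 2: what one permitted step allows**

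Take a Xyrem-naïve child with no pre-study dose, at the Table 1 maximum and still in the same weight band. The new dose is the Table 1 maximum plus 1.5 g, and the excess is 1.5 divided by that maximum.

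- Under 30 kg: 6 + 1.5 = 7.5 g/night; 1.5 / 6 = 25% above the limit.
- 30 to under 45 kg: 7.5 + 1.5 = 9 g/night; 1.5 / 7.5 = 20% above the limit.

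An increase made after the child has grown into a higher band is not counted, because Table 1 would then allow it.

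**Step 3: the comparison**

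For the earlier entrant, the cap in Section 3.1.5 holds the dose at 6 or 7.5 g/night and forbids both increases. For the later entrant, and for any child in Part 2 after titration, no sentence forbids them. The uncapped periods last 38 to 45 weeks of Part 1 for Xyrem-naïve entrants and up to 2 years of Part 2. These are the lengths of the periods, not time spent above a limit.

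**The case against.** The best opposing reading is that Section 3.1.5 is the section on the whole Open-Label Safety Period, that its cap stands beside the 1.5 g step rule, and that Section 5.2 repeats the step rule for everyone as a short restatement. On that view the cap was always general, and it appears under the earlier-entrant sub-heading only because those subjects restart at a reduced dose. This is plausible as to intent. As to wording it fails: Sections 7.1.5 and 7.2.5 divide subjects by Amendment 4 and give the cap to one branch only.

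Three other points stand and limit the finding.

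- Table 1 is not an absolute limit. Criterion 8 admits a child of any weight on up to 9 g/night, and the cap itself lets a higher pre-study dose prevail. Both example doses lie within 9 g/night.
- A later Xyrem-naïve child starts the open-label year on a dose already optimized under Table 1, so exceeding it takes a deliberate decision by the investigator.
- Other controls may exist. Drug is dispensed through an interactive system with sponsor dosing instructions that are not shown, adverse-event removal rules apply, and the DSMB reviews respiratory depression and depressed consciousness.

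A reader might also infer that children of 45 kg or more could be taken above 9 g/night. The open-label text does not forbid it for later entrants, but whether such a dose could be measured or dispensed cannot be judged without the syringe figure and the dosing instructions.

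**Conclusion.** The gap is real and should be closed. As written, a later Xyrem-naïve child under 45 kg, or such a child in Part 2 after titration, may be raised 20% to 25% above the limit set for an otherwise identical earlier child. This assumes a start at the Table 1 maximum, no change of weight band, no pre-study dose and one 1.5 g step. The number of children affected is unknown.

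Three stronger conclusions are not supported. First, Section 1.1.1.1 reports that adult blood levels rise 3.7-fold when the dose doubles from 4.5 to 9 g, so a reader might infer a specific, larger rise in exposure. That is one adult two-point figure, and the protocol states that no pediatric PK data existed, so exposure in children is unknown. Second, nothing shows that the sponsor intended an uncapped regimen; a drafting omission when the cap text was split by Amendment 4 is the likelier explanation, though that is an inference. Third, the randomized efficacy comparison is unaffected, because the gap lies wholly in open-label dosing after it.

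**What to change.** State one ceiling in Section 5.2 and mirror it in Sections 3.1.5 and 3.1.8 and in the post-Amendment 4 bullets of Sections 7.1.5 and 7.2.5. For every subject in the Open-Label Safety Period and Part 2, the total nightly dose must not exceed the higher of (a) the Table 1 maximum for current weight and (b) the stable dose before study entry, and must never exceed 9 g/night. For re-enrollers already on Xyrem, (b) should be the stable dose at Part 2 Screening. Without that allowance the cap would conflict with criterion 20, which admits such children on up to 9 g/night whatever their weight.

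For children with no qualifying earlier dose, the limits become 6, 7.5 and 9 g/night by weight band. The cost is one sentence in five places and possibly a dose review for a few subjects already above the limit. No new data, design change or sample-size change is needed.
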